# 13 QUALITY CONTROL AND QUALITY ASSURANCE

Study medications will be Health Canada-approved following Good Manufacturing Practice.

## 14 ETHICS/PROTECTION OF HUMAN SUBJECTS

#### 14.1 Ethical Standard

This study is to be conducted in the spirit of Canadian and international standards of Good Clinical Practice (International Conference on Harmonization guidelines), Declaration of Helsinki, and International Ethical Guidelines for Biomedical Research Involving Human Subjects, applicable provincial regulations and institutional research policies and procedures. All investigators must have received ethics and GCP training prior to human subject involvement.

#### 14.2 Institutional Review Board

Prior to the initiation of the study, the protocol, all informed consent forms, and the participant Information materials will be submitted to and approved by the RI-MUHC. For outside of Quebec, other REBs will take responsibility for their provinces using this master protocol. Likewise, any future amendments to the study protocol will be submitted and approved by the IRB before implementation. This protocol and any amendments will undergo review and approval.

#### **14.3** Informed Consent Process

• Written informed consent will be obtained via an English or French-language, internetbased web form. If potential participants have questions, they may contact a study staff

- member in their province to answer their questions about the research, either via email or phone call. Participants will electronically sign the consent form.
- Participants will be asked to upload a photo ID (provincial health card) to confirm their identification.
- After completion of reading the form, participants will be assessed for comprehension, querying:
  - Concept of Randomization to ciclesonide or placebo
  - Whether ciclesonide is known to be effective in preventing disease
  - Duration of the study? (14 days)
  - Duration of taking the study medicine (14 days)
  - When follow up surveys will be sent (Days 1, 3, 5, 7, 10, and 14)
  - o If ciclesonide can be shared? (No)

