#### **3.2.2** Secondary Outcome Measures

- a) Hospitalization for SARS-CoV-2 related illness at day 14
- b) Primary outcome (proportion of patients with no cough, fever or dyspnea) measured at day 14
- c) Mortality at day 14 and 29
- d) Ordinal Scale for Evaluating subject Clinical Status (overall feeling) (see Appendix 2) measured on day 0, 1, 3, 5, 7, 14 and 29: We will evaluate the proportion who are reporting that they are "very much improved" or "much improved" by day 7 and day 14 (vs. not).
- e) PROMIS dyspnea, anxiety and sleep (respectively). We will look at the questionnaires at day 7 and at day 14 and compare the proportions between groups with a 3 point or higher change (compared to day 0 and using the t-score adjusted for population). We will also report the mean T scores. Raw scores are converted to standardized T scores using

- calibrated algorithms for the general population. They are standardized scores with a mean of 50 and SD of 10; 45 to 55 on a PROMIS T score is considered the normal range. 55-60 is mild levels of symptoms (anxiety, sleep, dyspnea), 60-70 is moderate, and 70+ is severe. A meaningful change will be considered a 3 point change on the T score.
- f) Visual Analog scale from 0-10 indicating improvement in symptoms measured at day 0, 1, 3, 5, 7, 10, 14 and 29; analysis will look at resolution of symptoms at day 7 and day 14, and resolution of cough at day 7 and 14.
- g) Time to symptom resolution (post-hoc)

Assessment of outcome measures will be primarily by self-report. As necessary, COVID-19 disease will be verified from public health records, medical records, or death certificates. The primary analysis will use PCR+ confirmed disease.

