## 4.2 Study participant duration

- 14 days consisting of internet-based virtual visits
- Observational follow up at day 29 to assess final outcome status of hospitalization and SAE.

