#### **9.2.3** Serious Adverse Events (SAEs)

SAEs (e.g. hospitalization) will be followed for up to 29 days to assess final outcome.

A patient who reports hospitalization and/or an adverse effect of the study drug on a CRF who has not reached out to the team by phone or email will be contacted in a timely fashion and the site doctor made aware. We will review the "positive" CRFs to detect these. We also collect details about the hospitalization.

Patients who do not complete their day 14 CRF will receive reminder emails and, if they do not respond to that, they will be telephoned. Patients must provide an alternate contact at enrollment. If they do not respond to the above means, we will call that contact to find out what has happened. If that person does not know or is not available, we will send registered mail to the address of the patient before concluding loss to follow-up. A sensitivity analysis of the mortality outcome will be performed assuming patients lost to follow-up despite these means have died.

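### The consent comprehension check ends the study at Day 14 and the chase for non-responders is tied to the Day 14 form, although vital status and SAE follow-up run to Day 29

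*Combined protocol and SAP*

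**What the plan says.** **Comprehension check (14.3).** After reading the consent form, participants are tested on several items. One is "Duration of the study? (14 days", followed by a separate item on how long the medicine is taken, also 14 days. Another is "When follow up surveys will be sent (Days 1, 3, 5, 7, 10, and 14", which has no Day 29.

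**Follow-up elsewhere in the protocol.**
- Section 3.2.2 lists "Mortality at day 14 and 29" as a secondary outcome. The ordinal scale and visual analog scale are also collected at Day 29.
- Section 4.2 adds "Observational follow up at day 29 to assess final outcome status of hospitalization and SAE".
- The section 7 table marks nearly every questionnaire at Day 29, including hospitalisation/oxygen, side effects and mortality. Section 7.4 lists the Day 29 content again.
- Sections 9.2.3 and 9.4 follow SAEs for up to 29 days.
- The Summary gives both a Day 29 assessment and follow-up to 30 days.

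**Retrieval of non-responders (9.2.3).** "Patients who do not complete their day 14 CRF will receive reminder emails and, if they do not respond to that, they will be telephoned". An alternate contact and registered mail follow before loss is concluded. The same paragraph ends: "A sensitivity analysis of the mortality outcome will be performed assuming patients lost to follow-up despite these means have died".

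**Other routes to the data.** Section 3.2.2 allows verification from public health records, medical records or death certificates. Section 4.3 provides for medical-record access, and 8.2 for permission to contact health authorities or a provider on loss to follow-up. Section 9.3.1 and Appendix A give participants still in hospital at Day 14 one more form 14 days later.

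**The concern.** The comprehension check exists to confirm what a participant has understood before signing electronically. Here the answers it accepts disagree with the schedule. A participant who passes has been told that the study is over at Day 14 and that no survey follows.

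The trial has no visits; its procedures are self-reported online questionnaires. A participant who believes the study has ended is less likely to answer at Day 29, and 9.2.3 gives staff no instruction to pursue that form. For mortality this matters more than for a symptom score. A participant who dies at home between Day 15 and Day 29 appears in the database as a form that was not returned, the same as someone who lost interest. Without a chase the two cannot be told apart.

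The sensitivity analysis that counts lost patients as dead is meant to cover this situation, but 9.2.3 does not say at which time point it is applied.

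**Working it through.** No figure in the plan bears directly on this point, so the main check sets the passages side by side.

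**1. Can 14 days be read as treatment length?** No. Treatment duration is its own item in 14.3. The study-duration item must mean something else, and its answer is still 14 days.

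**2. What the check leaves out.**
- Days beyond the tested duration: 29 − 14 = 15, and 15/29 = 0.52, or 52% of follow-up.
- Post-baseline surveys in the section 7 table: Days 1, 3, 5, 7, 10, 14 and 29, so seven. Surveys in 14.3: six. The missing one is the final one.

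**3. What happens to a missing form after Day 14.**

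| Situation | Procedure stated |
|---|---|
| Day 14 form missing | Email, telephone, alternate contact, registered mail (9.2.3) |
| In hospital at Day 14 | Extra form 14 days later (9.3.1, Appendix A) |
| Hospitalised or SAE | Followed up to Day 29 (9.2.3, 9.4) |
| Day 14 form returned, Day 29 form missing, no known event | None; records and provider contact permitted, no trigger (3.2.2, 4.3, 8.2) |

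The last row is the gap.

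**4. How the lost-as-dead rule can be read.** It covers patients lost "assuming patients lost to follow-up despite these means have died", where the means are the steps triggered by the Day 14 form.
- *Day 14 only.* A participant who answers at Day 14 and is silent at Day 29 is not counted as dead. Day 29 mortality then has no stated rule for these participants.
- *Day 29 as well, with the steps extended.* This is coherent, but it is not written.
- *Day 29 as well, without the steps.* Silent participants would be counted as dead without having been pursued. The text does not say this either.

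**5. Illustration only.** The documents give no Day 29 loss rate. The denominator is the 159 per arm of 11.2. The standard two-proportion formula with 65% against 80%, 80% power and two-sided 5% alpha gives 138 per arm (276 in total, as in the table), and 138 × 1.15 = 158.7, rounded to 159. Under the second or third reading, the number per arm imputed as dead is 159 × loss rate:

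| Assumed unresolved loss at Day 29 | Per arm |
|---|---|
| 5% | 8.0 |
| 10% | 15.9 |
| 15% | 23.9 |
| 25% | 39.8 |

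The 15% and 25% appear in the protocol as dropout allowances (11.2 and 5.3.3), not as forecasts of unresolved Day 29 loss. The 5% and 10% are assumptions.

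**The case against.** **The 14 days follow the protocol's own split.** Section 4.2 describes 14 days of virtual visits and sets Day 29 apart as observational; 7.4 treats Day 14 as the final visit. This explains how the wording arose. It does not rescue the survey list, which omits a scheduled questionnaire, or remove the fact that Day 29 collects a listed secondary outcome.

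**The consent form may state the Day 29 contact.** The consent pages are not available here, so this stands: the point concerns the comprehension check, and it does not follow that participants were misinformed overall. If the form is right, its own test contradicts it.

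**Day 29 outcomes are few.** This stands in part. A reader might infer that the hospitalisation endpoint runs to Day 29, but 3.2.2 places it at Day 14 only; hospitalisation at Day 29 is final-status and safety follow-up. The ordinal and visual analog scales are collected at Day 29 but analysed at Days 7 and 14. Mortality is the only listed secondary outcome with a stated Day 29 analysis time.

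**Other ways of finding out exist.** Records, death certificates and provider contact mean vital status need not depend on a returned form. They are permissions, though, used as necessary, with no Day 29 trigger.

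**The rule does not count unchased patients as dead.** This is correct on the text. A reader might infer that about 24 or 40 participants per arm would be counted as dead, and that unequal loss would pass for a mortality difference. The documents support neither. The rule reaches only those lost after the retrieval steps, and the percentages behind those counts are sample-size allowances or assumptions. That unequal loss moves the result is true of any lost-as-dead analysis. What remains is the unstated time point.

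**Little consenting may be left.** Section 9.5 reports in the past tense that enrolment dropped off, so the consent correction may reach few new participants. The retrieval and analysis corrections do not depend on new enrolment.

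**Conclusion.** The point holds. The comprehension check conflicts with the schedule on the end of follow-up and omits the last survey. The only stepwise retrieval procedure is triggered by the Day 14 form, and the lost-as-dead analysis has no stated time point. Followed as written, the plan exposes Day 29 vital status to missing data that a routine chase would reduce.

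The size that can be stated is 15 of 29 follow-up days and one of seven post-baseline surveys outside what participants are tested on. The number lost at Day 29, and any effect on the mortality comparison, cannot be estimated from the documents; the counts in the working table are illustration. The conclusion rests on reading 9.2.3 literally and assumes that no separate operating procedure, outside these documents, covers a missing Day 29 form.

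The Day 7 primary outcome and the sample size are untouched. This should be corrected, but it does not threaten the main result.

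**What to change.** 1. In 14.3, change the study-duration answer to follow-up through Day 29, leave the treatment-duration item as it is, and add Day 29 to the survey list. Reconcile the 30 days in the Summary with the Day 29 used elsewhere. Check that the consent form agrees.
2. In 9.2.3, apply the same retrieval steps to a missing Day 29 form, and name the use of records or provider contact (8.2) as a further step for vital status.
3. State whether the lost-as-dead analysis applies at Day 14, Day 29 or both. Apply it only to participants who have been through the retrieval steps.
4. Report missing vital status by arm at each mortality time point.

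**Cost.** Wording changes in the protocol and the electronic consent logic, an amendment, and some extra reminder calls and letters at Day 29 using contacts already collected. Where consenting is complete, items 2 to 4 carry the benefit; participants still in follow-up can be told of the Day 29 survey by email.

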#### 14.4 Exclusion of Women, Minorities, and Children

- Persons under 18 years of age are not eligible to participate.
- Women who are pregnant or breastfeeding are excluded because the safety data is inadequately known for this study.
- Non-English or French speaking adults are not eligible as the webpage and consents will only be available in English or French.

## **14.5** Subject Confidentiality

- Interaction will be via internet-based REDCap eCRFs conforming to required Canadian privacy and server security standards.
- Clinical data will be entered into a study specific database by designated staff on a regular basis from completed electronic Case Record Forms (eCRF). Access to database will be given to authorized personnel only (members of the immediate study team). eCRF and trial documents will be kept in a secure database.
- Documentation, data and all other information generated will be held in strict confidence. No information concerning the study, or the data will be released to any unauthorized third party, without prior written approval of the participant except as necessary for monitoring by the IRB or public health authorities
- No participant identifying information will be disclosed in any publication or at any conference activities arising from the study.
- Anonymized data on demographics, survey responses and outcomes will be pooled with international collaborators subject to inter-institutional agreements.

#### **14.6** Future Use of Stored Specimens

• No specimens are to be collected.

# 15 DATA HANDLING AND RECORD KEEPING

# **15.1** Data Management Responsibilities

# **15.2** Data Capture Methods

• Data will be obtained via internet-based REDCap forms.

## **15.3** Types of Data

• Participants will be asked to provide data regarding COVID-19 exposure timing and location. They will also be asked to provide ongoing symptom reports during the follow-up period.

## **15.4** Timing/Reports

- An enrollment progress report will be generated monthly
  - o Participants Enrolled
  - o Participants on study
  - o Participants completed the study
  - o Lost to Follow Up
  - Cumulative Hospitalizations (pooled, both arms)
  - Cumulative mortality
- De-identified data will be shared with the research team members for analysis.

## 15.5 Study Records Retention

- No paper documents will be retained or stored.
- Digital records will be kept in a secure server setting.

#### **15.6** Protocol Deviations

Protocol violations will be reported to the IRB of record in each province and forwarded to the main Canadian PI.

# **16** Publication Policy

Publication will be expeditiously made with a full, de-identified data made available.

[figure not shown]

#### SUPPLEMENTS/APPENDICES

#### **APPENDIX A: SCHEDULE OF EVENTS**

#### **Overview of Study Procedures**

Participants with ongoing hospitalization at day 14 will be followed with an additional eCRF after 14 days.

## **APPENDIX B: LOGIC**

- 1) Must have all inclusion criteria as defined.
- 2) Must not have any exclusion criteria.
- 3) Patients who are not in the study provinces will receive a message saying the study is not available in their province (this is not counted as being formally ineligible).
